4.2. Exclusion criteria

- Unable to provide informed consent
- Requires LTOT, defined by need for resting oxygen in the opinion of the local investigator
- Life expectancy <6 months
- On the active transplant list
- Previous acidotic hypercapnic respiratory failure (AHRF) requiring non-invasive ventilation (NIV)

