8.2.2.3 Mechanistic

Haemoglobin and haematocrit, which are measures of secondary effects of chronic hypoxia – rises in either would indicate a lack of effectiveness of AOT, or disease progression by way of development of chronic respiratory failure. They are a required safety measure as well, as development of secondary rises in either measure would be an indication for routine oxygen treatment.

Physical activity data will also be obtained via an accelerometer in a subset of 20% of trial participants (n=52; 26 participants from each trial arm), and associated processing software for how many minutes per day somebody is active in terms of intensity of exercise: sedentary; low; moderate; high. Accelerometers will be worn by the participant for 7 days after randomisation prior to commencing the trial allocation. It will then also be worn for 7 days prior to their final trial visit.

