11.4.1. Serious Adverse Events not requiring reporting to the Trial Office

At whatever time they occur during an individual's participation, from when intervention started to end of participant follow-up, the following are not considered to be critical to evaluations of the safety of the trial:

1. Pre-planned hospitalisation even if >24 hours
2. Hospital admissions lasting less than 24 hours

All events which meet the definition of serious must be recorded in the participant notes, including the causality and severity, throughout the participant's time on trial, including follow-up, but for trial purposes these events do not require reporting on the SAE Form. Such events are "safety reporting exempt".

11.4.2. Serious Adverse Events requiring non-expedited reporting to the Trial Office (expected SAEs)

OXYPuF participants are likely to have significant co-morbidities and therefore the frequency of SAEs may be high. Most of the SAEs occurring in OXYPuF will be anticipated in the sense that they are recognised and accepted complications/consequences of IPF.

The events outlined in Table 4 are regarding as expected SAEs, i.e. are recognised complications/consequences of IPF. These events should be reported in the participant's medical

records and on the OXYPuF SAE Form, and will not be subject to expedited reporting i.e. within 24 hours of the event, but should be reported within 2 weeks of the site research team becoming aware of these events. As such events will, by protocol definition be unrelated, rapid assessment of causality is not required.

Table 4 Expected SAEs that do not require expedited reporting

Acidotic hypercapnic respiratory failure
Right heart failure
Polycythaemia

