11.5.2. Assessment of expectedness of an SAE by the CI

The CI will also assess all related SAEs for expectedness with reference to the criteria in table 6.

Table 6: Categories of expectedness

Category	Definition
Expected	An adverse event that is consistent with known information about the trial related procedures or that is clearly defined in the relevant safety information found in the Baywater Medical Oxygen SmPC.
Unexpected	An adverse event that is not consistent with known information about the trial related procedures.

If the event is unexpected (i.e., it is not defined in the approved version of the Reference Safety Information (RSI)) it will be classified as a Suspected Unexpected Serious Adverse Reaction (SUSAR).

The CI will undertake review of all SAEs and may request further information from the clinical team at site for any given event(s) to assist in this.

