12.2 Case Report Form (CRF) completion

The CRFs will include (but will NOT be limited to) the following Forms (see Table 8).

Table 8: Case report forms in OXYPuF

Form Name	Schedule for submission
Consent CRF	At the point of randomisation
Randomisation CRF	At the point of randomisation
Actigraph CRF	At the point of randomisation

Baseline and follow-up CRFs including participant reported outcome measures	As soon as possible after each assessment time point
Serious Adverse Event CRF paper CRF only	If expedited: emailed within 24 hours of site research team becoming aware of event If non-expedited: emailed within 4 weeks of site research team becoming aware of event
Change of status CRF	As soon as possible after the point of reduced participation or death

A CRF is required and should be completed for each individual participant. The data held on the completed original CRFs are the sole property of the respective PIs whilst the data set as a whole is the property of the Sponsor and should not be made available in any form to third parties except for authorised representatives or appropriate regulatory authorities without written permission from the Sponsor.

Data reported on each CRF will be consistent with the source data and any discrepancies will be explained. All missing and ambiguous data will be queried. Staff delegated to complete CRFs will be trained to adhere to the **OXYPuF Work Instruction on CRF completion** which can be found in the **OXYPuF ISF**.

The delegated staff completing the CRF should ensure the accuracy, completeness and timeliness of the data reported. This will be evidenced by signing and dating the CRF.

The following guidance applies to data and partial data:

- Only CRFs provided by the Trial Office should be used.
- Original completed CRFs or true copies should be sent to the Trial Office with copies filed in the ISF.
- Entries should be made in dark ink and must be legible.
- Any errors should be crossed out with a single stroke, the correction inserted and the change initialled and dated.
- Time format – all times should be in accordance with the 24hr clock

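### Section 11.4.2 rules the Table 4 serious adverse events unrelated in advance, against the causality assessment in section 11.5.1, and their reporting deadline is given as both 2 and 4 weeks

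*Protocol*

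**What the plan says.** Section 11.4.2 of the protocol sets up a slower reporting route for three SAEs, listed in Table 4: AHRF, right heart failure and polycythaemia. The ground for the list is the disease: "The events outlined in Table 4 are regarding as expected SAEs, i.e. are recognised complications/consequences of IPF". The events still go on the SAE form, but not within 24 hours. The reason given is: "As such events will, by protocol definition be unrelated, rapid assessment of causality is not required".

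Section 11.5.1 describes what happens to an SAE form. The investigator states causality on a five-category scale, and the Chief Investigator then reviews causality independently. If either judges the event related, it is a SAR, and the Chief Investigator may not downgrade the investigator's view.

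Section 11.5.2 adds the next step: "The CI will also assess all related SAEs for expectedness with reference to the criteria in table 6". Table 6 ties expectedness to the product information for medical oxygen. Section 11.6 then sends SARs to the annual safety report and SUSARs to the regulator, the ethics committee and the sponsor's governance team within 7 or 15 days.

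On timing, section 11.4.2 says of the Table 4 events that they are not expedited, "but should be reported within 2 weeks of the site research team becoming aware of these events". Table 8 in section 12.2 says of the SAE form: "If non-expedited: emailed within 4 weeks of site research team becoming aware of event".

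**The concern.** Two separate judgements have been merged. Whether an event is expected in patients with this disease bears on how urgently a report is needed. Whether the trial treatment caused a particular event is a question about that case. Section 11.4.2 answers the second question for all three events, in both arms, before any has occurred.

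What is at stake is the related-event pathway. Everything after the SAE form (SAR status, the expectedness check, SUSAR status, the annual safety report and the 7- and 15-day reports) starts from a judgement that an event is related. If sites take the wording of 11.4.2 as their instruction, that judgement is never made for these events. A count of related events would then be partly a product of the rule.

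The second fault is simpler: a site has two deadlines for the same form.

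**Working it through.** Apart from the deadlines this is a comparison of text, so the sections are set side by side.

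**1. Basis of the list.** Table 4 rests on what the disease does (11.4.2). Expectedness of a reaction rests on what the product information for oxygen says (Table 6; the definition of an unexpected adverse reaction in Table 3 uses the same basis). An event can be common in pulmonary fibrosis and still, in one patient, be a reaction to oxygen. Table 4 membership therefore cannot settle causality.

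**2. Causality of a Table 4 event.**
- 11.4.2: unrelated, by definition.
- 11.5.1: whatever the investigator and the Chief Investigator each conclude; either can make it related. No exception is made for Table 4.
- 11.4.1: causality of every event meeting the definition of serious is to be recorded in the notes, including events that need no report at all. Section 11.5.1 applies its causality categories to those exempt events too.

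These cannot all hold. As written, an admission of under 24 hours gets a case-by-case causality entry, while AHRF on trial oxygen has its answer supplied in advance.

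**3. What follows if 11.4.2 is applied.** Unrelated under 11.4.2 → not a SAR under 11.5.1 → not assessed for expectedness under 11.5.2 → not in the SAR content of the annual report and not a SUSAR under 11.6. The protocol does not say how a Table 4 event that an investigator believes to be related should leave the slow route.

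**4. Which event matters most.** Section 4.2 excludes patients with previous AHRF that required non-invasive ventilation. The protocol gives no reason, but it screens out that history before allocating oxygen and then declares the same event unrelated when it occurs on the trial.

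**5. Deadlines.** Section 11.4.2 gives 2 weeks = 14 days. Table 8 gives 4 weeks = 28 days. Ratio 28/14 = 2.

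The longest time from site awareness to the regulator, if a Table 4 event were classed as a SUSAR, is the site deadline plus the section 11.6 clock. This assumes that the clock starts when the Trial Office receives the form.
- Fatal or life-threatening (7 days): 14 + 7 = 21 days, or 28 + 7 = 35 days.
- Other (15 days): 14 + 15 = 29 days, or 28 + 15 = 43 days.
- On the 24-hour route, for comparison: 1 + 7 = 8 days and 1 + 15 = 16 days.

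**The case against.** The best defence is that 11.4.2 waives only the speed of causality assessment, not the assessment itself. The form is still completed, 11.5.1 still asks the investigator for causality on it, and 11.5.2 has the Chief Investigator review all SAEs. This stands in part. A reader might infer from 11.4.2 that these events can never become SARs, but that follows only if 11.4.2 overrides 11.5.1, and the protocol does not say that it does. What remains is that the reason given for the waiver is a ruling on causality, in the section a site would consult for exactly these events.

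A reader might also infer that Table 4 holds the three events most likely to be caused by oxygen. The protocol does not support that. It treats haemoglobin and haematocrit as markers of chronic hypoxia, where "rises in either would indicate a lack of effectiveness of AOT, or disease progression by way of development of chronic respiratory failure", and it calls them a safety measure because a rise would be a reason to give oxygen. The background section describes long-term oxygen as protecting against pulmonary hypertension and cor pulmonale. Only AHRF has support as an oxygen hazard, and that is indirect, through the exclusion criterion.

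Nor does it follow that serious harm would disappear from the results. Section 15.2.2 compares the number of patients with SAEs by arm, with a descriptive table and no causality filter, so an excess of AHRF on oxygen would still be visible there. The Data Monitoring Committee may review any SAE and is supplied with safety outcomes.

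Finally, the product information for oxygen is not at hand. If it lists one of these events, a related case would be expected and so not a SUSAR under any wording. It would still be a SAR and belong in the annual report.

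**Conclusion.** The protocol is wrong as written on two points.

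First, 11.4.2 treats expectedness in the disease as proof that oxygen was not the cause, and it contradicts 11.5.1 (and the recording rule in 11.4.1). Where 11.4.2 is followed, every Table 4 event is classed as unrelated whatever the facts and drops out of the SAR/SUSAR pathway. Where 11.5.1 is followed, it does not. Sites could differ, and relatedness data for these events would be uninterpretable. The effect is limited to relatedness classification and onward reporting; the primary outcome and the by-arm SAE comparison are untouched. The number of events affected cannot be given, because the protocol states no expected rates. That any SUSAR would be missed is unproven, since it depends on the oxygen product information.

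Second, the deadline for the same report is 14 days in one place and 28 in another. This needs no assumption. It is a separate inconsistency and adds no weight to the first point.

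**What to change.** - In 11.4.2, delete the clause that declares Table 4 events unrelated. State that listing in Table 4 affects reporting speed only, and that the investigator and the Chief Investigator assess causality under 11.5.1 for every Table 4 event.
- State how a Table 4 event judged related by either of them enters the SAR/SUSAR pathway, including the reporting time that then applies. The sponsor should choose the route; the present text has none.
- Reconcile 11.4.2 and Table 8 to a single deadline for non-expedited reports, and carry it into the SAE form instructions.

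The cost is a protocol wording amendment and a line on the SAE form. No new data are collected: the form is already required for these events and already asks for causality. If recruitment has begun, Table 4 events already reported should be checked for a causality entry made on its merits.

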11.4.3. Serious Adverse Events requiring expedited reporting to the Trial Office

All SAEs not listed in section 0 must be reported to the Trial Office on a trial specific SAE form within 24 hours of the site research team becoming aware of the event.

11.5. SAE Reporting process

On becoming aware that a participant has experienced an SAE which requires reporting on an SAE form, the PI or delegate should report the SAE to their own Trust in accordance with local practice and to the Trial Office.

To report an SAE to the Trial Office, the PI or delegate must complete, date and sign the OXYPuF SAE form. The completed form together with any other relevant, appropriately anonymised, data should be submitted to the Trial Office using the information below in accordance with the timelines given in Section 0 and 0.

To report an SAE, submit the SAE Form to:

[contact]

Where an SAE Form has been completed by someone other than the PI initially, the original SAE form must be countersigned by the PI to confirm agreement with the causality and severity assessments.

On receipt of an SAE form, the Trial Office will allocate each SAE a unique reference number and notify the site via email to the site as proof of receipt. The site and the Trial Office should ensure that the SAE reference number is quoted on all correspondence and follow-up reports regarding the SAE and filed with the SAE in the ISF.

If the site has not received confirmation of receipt of the SAE or if the SAE has not been assigned a unique SAE identification number within 1 working day of reporting, the site should contact the Trial Office.

11.5.1. Assessment of causality of an SAE

When completing the SAE form, the PI (or, throughout this section, a medically qualified delegate) will be asked to define the nature of the seriousness and causality (relatedness; see table 5) of the event.

In defining the causality the PI must consider if any concomitant events or medications may have contributed to the event and, where this is so, these events or medications should be reported on the SAE form. It is not necessary to report concomitant events or medications which did not contribute to the event.

As per table 5, all events considered to be 'possibly', 'probably', or 'definitely' related to the intervention will be reported by the trial office as 'related'; all events considered at site to be 'unlikely' or 'unrelated' to the intervention will be reported by the trials office as 'unrelated'. The same categorisation should be used when describing AEs and protocol-exempt SAEs in the source data.

Table 5: Categories of causality

Category	Definition	Causality
Definitely	There is clear evidence to suggest a causal relationship, and other possible contributing factors can be ruled out.	Related
Probably	There is evidence to suggest a causal relationship, and the influence of other factors is unlikely.	
Possibly	There is some evidence to suggest a causal relationship. However, the influence of other factors may have contributed to the event (e.g., the participant's clinical condition, other concomitant events or medication)	
Unlikely	There is little evidence to suggest there is a causal relationship. There is another reasonable explanation for the event (e.g., the participant's clinical condition, other concomitant events or medication).	Unrelated
Not related	There is no evidence of any causal relationship.	

On receipt of an SAE Form, the Trial Office will forward it, with the unique reference number, to the Chief Investigator (CI) who will independently* review the causality of the SAE. An SAE judged by the PI or CI to have a reasonable causal relationship ("Related" as per Table 5) with the intervention will be regarded as a related SAE (i.e., SAR). The severity and causality assessment given by the PI will not be downgraded by the CI. If the CI disagrees with the PI's causality assessment, the opinion of both parties will be documented, and where the event requires further reporting, the opinion will be provided with the report.

*Where the CI is also the reporting PI an independent clinical causality review will be performed.

11.5.2. Assessment of expectedness of an SAE by the CI

The CI will also assess all related SAEs for expectedness with reference to the criteria in table 6.

Table 6: Categories of expectedness

Category	Definition
Expected	An adverse event that is consistent with known information about the trial related procedures or that is clearly defined in the relevant safety information found in the Baywater Medical Oxygen SmPC.
Unexpected	An adverse event that is not consistent with known information about the trial related procedures.

If the event is unexpected (i.e., it is not defined in the approved version of the Reference Safety Information (RSI)) it will be classified as a Suspected Unexpected Serious Adverse Reaction (SUSAR).

The CI will undertake review of all SAEs and may request further information from the clinical team at site for any given event(s) to assist in this.

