11. ADVERSE EVENT REPORTING

11.1 Definitions

Standard definitions of different types of adverse events (AEs) are listed in Table 3.

Table 3: Adverse event reporting definitions

Severity Definitions	Mild	Awareness of signs or symptoms that do not interfere with the participant's usual activity or are transient and resolved without treatment and with no sequelae.
	Moderate	A sign or symptom, which interferes with the participant's usual activity.
	Severe	Incapacity with inability to do work or perform usual activities.
Adverse Event	AE	
Any untoward medical occurrence in a participant administered a medicinal product and which does not necessarily have a causal relationship with this intervention.
 
Comment:
 
An AE can therefore be any unfavourable and unintended sign (including abnormal laboratory findings), symptom or disease temporally associated with the use of an investigational medicinal product, whether or not related to the investigational medicinal product.

Adverse Reaction	AR	All untoward and unintended responses to an IMP related to any dose administered. Comment: An AE judged by either the reporting Investigator or Sponsor as having causal relationship to the IMP qualifies as an AR. The expression reasonable causal relationship means to convey in general that there is evidence or argument to suggest a causal relationship.
Serious Adverse Event	SAE	Any untoward medical occurrence or effect that: Results in death Is life-threatening* Requires hospitalisation or prolongation of existing hospitalisation Results in persistent or significant disability or incapacity Is a congenital anomaly/birth defect Or is otherwise considered medically significant by the Investigator**
Serious Adverse Reaction	SAR	An AR which also meets the definition of a SAE.
Unexpected Adverse Reaction	UAR	An AR, the nature or severity of which is not consistent with the applicable product information (e.g., Investigator Brochure for an unapproved IMP or (compendium of) Summary of Product Characteristics (SmPC) for a licensed product). When the outcome of an AR is not consistent with the applicable product information the AR should be considered unexpected.
Suspected Unexpected Serious Adverse Reaction	SUSAR	A SAR that is unexpected i.e., the nature, or severity of the event is not consistent with the applicable product information. A SUSAR should meet the definition of an AR, UAR and SAR.

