Unexpected Event	UE	The type of event that is not listed in the protocol as an expected occurrence.
Related and Unexpected Serious Adverse Event	N/A	A SAE that meets both the definition of a Related and Unexpected Event.

* The term life-threatening is defined as diseases or conditions where the likelihood of death is high unless the course of the disease is interrupted.

** Medical events that may not be immediately life-threatening or result in death or hospitalisation but may jeopardise the participant or may require intervention to prevent one of the other outcomes listed in the definitions above.

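### Section 11.5.2 contradicts itself on expectedness: Table 6 uses a different test from the SUSAR sentence beneath it and from Table 3

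*Protocol*

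**What the plan says.** Protocol section 11.5.2 names the rule to be used: "The CI will also assess all related SAEs for expectedness with reference to the criteria in table 6". Table 6 has two rows.

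- **Expected:** "An adverse event that is consistent with known information about the trial related procedures or that is clearly defined in the relevant safety information". The safety information is that in the named medical oxygen SmPC. The two routes are joined by an or, so either is enough.
- **Unexpected:** an event that is not "consistent with known information about the trial related procedures". This row mentions neither the SmPC nor severity.

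The sentence directly below Table 6 explains unexpected differently, as meaning that "it is not defined in the approved version of the Reference Safety Information (RSI"), and classifies such an event as a SUSAR.

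Table 3 in section 11.1 defines an unexpected adverse reaction as "An AR, the nature or severity of which is not consistent with the applicable product information", and a SUSAR as "A SAR that is unexpected i.e., the nature, or severity of the event is not consistent with the applicable product information". Neither definition refers to trial procedures.

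Section 11.5.1 settles which events reach this step. An SAE judged to have a reasonable causal relationship "with the intervention will be regarded as a related SAE (i.e., SAR"). Relatedness is thus to the intervention, not to trial procedures.

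Section 11.6 ties reporting to the SUSAR label. Fatal or life-threatening SUSARs go to the MHRA, REC and the sponsor's research governance team (RGT) within 7 days, and other SUSARs within 15 days. All SUSARs are notified to site PIs. A serious adverse reaction that is not a SUSAR goes to the MHRA, REC and RGT in the annual Development Safety Update Report (DSUR).

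**The concern.** One judgement, expected or unexpected, decides whether a serious reaction to oxygen goes out in days or waits for the annual report. The protocol gives that judgement two different reference standards within one short section, and the one it explicitly calls the criteria departs from the trial's own SUSAR definition.

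The trial-procedures route also fits poorly with what is being judged. Only events already considered related to the intervention reach Table 6. A suspected reaction to oxygen could then be called expected because it resembles a known effect of a trial procedure, although the oxygen safety information says nothing about it. For illustration only: section 9 has participants do an exercise test both on and off oxygen. A serious event in such a test, judged possibly related to oxygen, might fit what is known about exercise testing and yet be absent from the SmPC.

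At stake are the timing of reports to the MHRA, REC and RGT, the SUSAR notice to PIs, and whether two assessors would classify the same event alike.

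**Working it through.** No sample size, error rate or event count enters this point, and the protocol states no figure to reproduce. The check is to classify a related SAE under each text. The inputs are the two rows of Table 6 and the sentence below them (section 11.5.2), the definitions in Table 3 (section 11.1), and the meaning of related (section 11.5.1). One assumption is needed: that the RSI is the safety information in the oxygen SmPC, as Table 6 implies.

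**Step 1. Nature of the event.** Cross two yes/no questions, which gives 2 × 2 = 4 combinations.

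| Fits procedure knowledge | In SmPC/RSI | Table 6 | Sentence below Table 6 | Table 3 |
|---|---|---|---|---|
| Yes | Yes | Expected | Expected | Expected |
| Yes | No | Expected (procedures route) | Unexpected, SUSAR | Unexpected, SUSAR |
| No | Yes | Meets both rows | Expected | Expected |
| No | No | Unexpected | Unexpected, SUSAR | Unexpected, SUSAR |

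Two of the four combinations are consistent and two are not.

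**Step 2. Direction of the error.**

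- Procedures yes, SmPC no: under Table 6 the event is not a SUSAR. Its route to the MHRA, REC and RGT changes from 7 or 15 days to the annual DSUR. This is possible under-reporting.
- Procedures no, SmPC yes: the other two texts make the event expected, so the annual DSUR is already its route. If the Unexpected row is applied, it would be expedited without need. This is possible over-reporting, not delay.

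**Step 3. Severity.** Take a reaction that the SmPC lists but that is more severe than described. Table 3 makes it unexpected, because severity alone is enough there. Table 6 has no severity test, so the SmPC route allows it to be filed as Expected. The sentence below the table asks whether the event is defined in the RSI and does not say whether severity counts. Here too expedited reporting can be missed.

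**Step 4. Frequency.** The number of affected events would be the number of related SAEs multiplied by the share in the under-reporting combination or the severity case. The protocol gives neither, so no estimate is offered.

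**The case against.** The best defence is that section 11.5.2 should be read as a whole. The only sentence there that assigns SUSAR status uses the RSI, and Table 3, to which section 11.2 sends the reader for definitions, agrees with it. A CI who follows that sentence would classify an event outside the RSI as a SUSAR whatever Table 6 says. This largely stands: a reader might infer that SUSARs will be lost, and the protocol does not show that. It does not remove the conflict, because the same section expressly directs the CI to Table 6, and because the sentence is silent on severity.

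The affected group may also be small. Events explained by a trial procedure will often be judged unlikely to be related to oxygen and so never reach Table 6. That is fair. Overlap remains possible through the possibly-related category, and its size is unknown.

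Three stronger readings are tempting and are not supported:

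- *That every inconsistent combination delays reporting.* Only one of the two does, together with the severity case.
- *That Table 3 adds a third standard for SUSARs through its Unexpected Event row* ("The type of event that is not listed in the protocol as an expected occurrence"). Table 3 builds a SUSAR from the definitions of adverse reaction, unexpected adverse reaction and serious adverse reaction. The Unexpected Event row belongs to a separate entry on related and unexpected SAEs.
- *That misfiled events would be seen only in the annual report.* An event judged under Table 6 has already reached the Trial Office on an SAE form and been reviewed by the CI. The DMC may review any SAE, and section 11.6 also sends other safety issues to PIs.

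**Conclusion.** The point holds as an internal contradiction in section 11.5.2, and between its Table 6 and Table 3. Two of four combinations are classified inconsistently. One of them, and any listed reaction more severe than described, can be filed as Expected under the named criterion. Such an event would miss 7- or 15-day reporting to the MHRA, REC and RGT and the SUSAR notice to PIs, while still reaching the Trial Office, the CI and the annual DSUR. In the other combination the risk is over-reporting.

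This rests on the RSI being the SmPC safety information, and on the CI applying Table 6 as instructed rather than the sentence beneath it. Frequency cannot be derived from the protocol. The correction is worth making because the rule governs expedited safety reporting, but the text does not show that any SUSAR would certainly be missed.

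**What to change.** Align both rows of Table 6 with Table 3 and with the RSI sentence, so that one reference decides expectedness:

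- **Expected:** the nature and severity of the event are consistent with the RSI.
- **Unexpected:** the nature or severity of the event is not consistent with the RSI.

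Delete the trial-procedures wording from both rows. The Unexpected Event row in Table 3 needs no change.

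The cost is a wording amendment to one table. A few more events may need expedited reporting: those that fit procedure knowledge but are outside the RSI, and listed reactions that exceed the described severity. In the other direction, events that are in the SmPC but do not fit procedure knowledge would no longer meet both rows.
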